2.2.2.5 Efficacy

No efficacy information is available as of 28 January 2016.

2.2.2.6 Drug Interactions

No formal drug interaction studies have been performed with LY3022855 in humans.

2.3 Vemurafenib

Vemurafenib is a low molecular weight, orally available inhibitor of some mutated forms of *BRAF* serine threonine kinase, including *BRAF* V600E. Vemurafenib also inhibits other kinases *in vitro* such as *CRAF*, *ARAF*, wild-type *BRAF*, *SRMS*, *ACK1*, *MAP4K5*, and *FGR* at similar concentrations. Some mutations in the *BRAF* gene including V600E result in constitutively activated BRAF proteins, which can cause cell proliferation in the absence of growth factors that would normally be required for proliferation. Vemurafenib has anti-tumor effects in cellular and animal models of melanomas with mutated *BRAF* V600E.

Vemurafenib has been FDA approved for patients with unresectable or metastatic melanoma with a *BRAF* V600E mutation and is commercially available. Please reference the FDA package insert for background information. Agent will be administered per standard of care guidelines in accordance with institutional standards and the FDA prescribing information.

2.4 Cobimetinib

Cobimetinib (Cotellic) is a reversible inhibitor of MAPK/ MEK1 and MEK2. MEK proteins are upstream regulators of the extracellular signal related kinase (ERK) pathway, which promotes cellular proliferation. *BRAF* V600E and K mutations result in constitutive activation of the BRAF pathway which includes MEK1 and MEK2. In mice implanted with tumor cell lines expressing *BRAF* V600E, cobimetinib inhibited tumor cell growth.

Cobimetinib and vemurafenib target two different kinases in the RAS/RAF/MEK/ERK pathway. Compared to either drug alone, co-administration of cobimetinib and vemurafenib resulted in increased apoptosis *in vitro* and reduced tumor growth in mouse implantation models of tumor cell lines harboring *BRAF* V600E mutations. Cobimetinib also prevented vemurafenib-mediated growth enhancement of a wild-type *BRAF* tumor cell line in an *in vivo* mouse implantation model.

Cobimetinib has been FDA approved for patients with unresectable or metastatic melanoma with a *BRAF* V600E or V600K mutation and is commercially available. Please reference the FDA package insert for background information. Agent will be administered per standard of care guidelines in accordance with institutional standards and the FDA prescribing information.

2.5 Rationale

The tumor microenvironment is known to play a role in innate or acquired resistance to BRAF inhibition^{29,30}. Tumor cells can control the surrounding milieu by producing cytokines that suppress cytolytic T-cells and recruit immunosuppressive cells, and CSF-1 is one such cytokine that is secreted by melanoma. CSF-1 induces the proliferation and differentiation of immunosuppressive myeloid cells, such as M2 polarized macrophages and myeloid-derived suppressor cells (MDSCs), by binding to CSF-1R on the surface of the cell. This results in the ability of the tumor cell to evade the immune response and allows for subsequent metastasis³¹.

Pre-clinical data by Mok et al. showed a dramatic reduction in tumor infiltrating myeloid cells when treated with CSF-1R inhibition. When this was combined with BRAF inhibition superior antitumor responses and increased tumor-infiltrating lymphocytes were observed³¹. Inhibitors to CSF-1R have been shown to deplete certain populations of TAMs and in established tumors, the combination of CSF-1R inhibitors with chemotherapy has been shown to dramatically enhance responses³².

Additional pre-clinical data from Wang et al. demonstrated that macrophages play a role in resistance to BRAF inhibitor therapy through paradoxical activation of the MAPK pathway leading to increased production of vascular endothelial growth factor (VEGF). Targeting macrophages in a pre-clinical model led to increased tumor activity of BRAF inhibition in mouse and human tumor models³³. These data together suggest that targeting macrophages in combination with BRAF inhibition in patients with melanoma may reduce baseline resistance and increase efficacy. Prior BRAF inhibition has also been shown to lead to increased TAMs, suggesting a potential role of combination therapy in patients with acquired resistance³⁴.

2.5.1 LY3022855 Flat Dosing Rationale

LY3022855 was initially dosed per body weight. However, Study JSCA (Version 7.0) was amended to explore a non-weight based dosing scheme based upon clinical data.

As of 14 August 2016, LY3022855 serum concentrations for non-compartmental analysis were available from 33 patients enrolled in Study JSCA within 7 cohorts: 0.3 mg/kg QW (N=4), 0.6 mg/kg QW (N=3), 1.25 mg/kg QW (N=5), 1.25 mg/kg every 2 weeks (Q2W) (N=11), 2.5 mg/kg QW (N=6), 100 mg QW (N=3), and 150 mg QW (N=1). The non-compartmental PK parameters stratified by dosing regimen and day of PK sample collection for Study JSCA are provided in **Table 8**. Mean LY3022855 serum concentration-time profiles on Day 1 and on Day 15 or 22 for Study JSCA are presented in **Figure 1**.

Table 8: Summary of Non-compartmental PK Parameters Following IV Infusion of Weight-Based and Non-Weight-Based of Dosing LY3022855 in Cancer Patients during Cycle 1 for Study JSCA

Geometric Mean

(CV%)

	0.3 mg/kg	0.6 mg/kg	1.25 mg/kg	1.25 mg/kg		2.5 mg/kg		100 mg		150 mg
Treatment QW QW QW		Q2W		QW		Q	QW			
Cohort	2	3	5	4		1		6a		7a
Day	1	1	1	1	15	1	22	1	84 or 99	1
N	4	3	5	11	10	6	4	3	2	1
Parameter										
C _{168h} , μg/mL	NC	NC		3.32	3.35	14.4	50		7.71 ^e	NC
			(5.68 and 3.41) ^a	$(11)^{b}$	(22) ^c	(34)	(25) ^d	(1.77 and 6.11) ^a		
$C_{max,} \mu g/mL$	6.83	13.5	26.0	30.7	30	69.2	92.7	34.6		42.7
	(32)	(33)	(14)	(24)	(25)	(13)	(23)	(25)	(42.8 and 31.2)	
t _{max} f, h	0.01	2.02	1.01	0.01	1.00	0.75	0.97	0.960		2.02
	(0.01-	(0.01-	(0.01-21.6)	(0.01-2)	(0.01-2)	(0.01-8.00)	(0.50-2.00)	(0.01-2)	(0.01 and 1.07)	
	1.02)	2.08)								
t _{1/2} ^g , h	30.9 ^d	30.8	58.3	41.4	46.9h	85.0	196	48.2	82.8e	38.7
	(25.2-44)	(23.6-	(45.5-85.3)	(21.5-67.3)	(24.3-109)	(56.6-126)	(132-346)	(35.9-69.9)		
		36.2)								
$C_{av,\tau}$, $\mu g/mL$	1.53 ^d	2.91	10.8	4.72	5.06 ^h	29.9	55.8	10.5	18.9e	13.2
	(15)	(24)	(21)	(50)	(49)	(18)	(41)	(28)		
$\mathrm{AUC}_{(0-\infty)}$,	264 ^d	500	2130	1600	1730^{h}	6860	21200	1970	4150e	2330
h·μg/mL	(17)	(24)	(28)	(50)	(52)	(26)	(73)	(37)		
$AUC_{(0-\tau)}^{i}$,	257 ^d	489	1810	1590	$1700^{\rm h}$	5030	9370	1770	3170e	2220
$h \cdot \mu g/mL$	(15)	(24)	(21)	(50)	(49)	(18)	(41)	(28)		
CL, L/h	0.107 ^d	0.0720	0.0561	0.0559	0.0516 ^h	0.0378	0.0203	0.0566	0.0315e	0.0676
	(21)	(30)	(31)	(33)	(36)	(25)	(34)	(28)		
V _{ss} , L	4.71 ^d	3.15	4.72	3.39	$3.37^{\rm h}$	4.67	5.70	3.88	3.68e	3.77
	(9)	(10)	(12)	(22)	(20)	(37)	(19)	(23)		
RA	NC	NC	NC	NC	1.04 ^{h, j}	NC	1.82 ^{c, k}	NC	2.29 ^{e, 1}	NC
					(18)		(27)			

Abbreviations: $AUC_{(0-\tau)}$ = area under the concentration versus time curve from time zero to τ ; $AUC_{(0-\infty)}$ = area under the concentration versus time curve from time zero to ∞ ; C_{168h} = serum concentration collected 168 hours following the start of infusion; $C_{avy\tau}$ = average serum concentration over dosing interval calculated using $AUC_{(0-\tau)}$; CL = total body clearance; C_{max} = maximum

Table 8: Summary of Non-compartmental PK Parameters Following IV Infusion of Weight-Based and Non-Weight-Based of Dosing LY3022855 in Cancer Patients during Cycle 1 for Study JSCA

Geometric Mean

(CV%)

[figure not shown]
						(0 1 70)				
	0.3 mg/kg	0.6 mg/kg	1.25 mg/kg	1.25 mg/kg		2.5 mg/kg		100 mg		150 mg
Treatment	QW	QW	QW	Q2W		QW		QW		QW
Cohort	2	3	5	4		1		6a		7a
Day	1	1	1	1	15	1	22	1	84 or 99	1
N	4	3	5	11	10	6	4	3	2	1

[figure not shown]
serum concentration; CV = coefficient of variation; h = hours; N = number of patients; NC = not calculable; Q2W = once every 2 weeks; QW = once weekly; $R_A = intrapatient$ accumulation ratio; $t_{1/2} = terminal$ elimination half-life; $t_{max} = time$ of maximum serum concentration; $V_{ss} = volume$ of distribution at steady-state.

- ^a N=2; reported as individual parameter estimates.
- b N=5.
- c N=4.
- d N=3.
- e N=1; reported as individual parameter estimate.
- f Median (Minimum Maximum).
- g Geometric Mean (Minimum Maximum).
- h N=9
- $\tau = 168 \text{ h}$ for QW regimen; $\tau = 336 \text{ h}$ for Q2W regimen.
- j $R_A = AUC_{(0-\tau),day 15} / AUC_{(0-\tau),day 15}$
- ^k $R_A = AUC_{(0-\tau),day 22} / AUC_{(0-\tau),day 1}$
- ¹ $R_A = AUC_{(0-\tau),day\ 84\ or\ day\ 99}/\ AUC_{(0-\tau),day\ 1.}$

LY3022855 in cancer patients exhibits pharmacokinetic properties consistent with those typically expected for an IgG1 antibody, with mean total body clearance (CL) after a single dose ranging from 0.0378 to 0.107 L/h, mean volume of distribution at steady state (V_{ss}) after a single dose ranging from 3.15 to 4.72 L, and mean half life (t_{1/2}) after a single dose ranging from 30.8 to 85.0 hours. LY3022855 CL appears to be non-linear with respect to dose, with higher doses of LY3022855 exhibiting lower CL values (**Figure 2**). These results are in accordance with the previous PK analysis for Cohorts 1 to 5, as detailed in the Investigator's Brochure.

[figure not shown]

Abbreviations: h = hours; N = number of patients treated; QW = once weekly; Q2W = once every 2 weeks.

Figure 1: Mean concentration-versus-time profiles for LY3022855 following intravenous administration to patients with cancer on Day 1 (upper panel) and on Days 15 and 22 (lower panel) for Study JSCA.

Abbreviations: N = number of patients treated; QW = once weekly; Q2W = once every 2 weeks.

Figure 2: Individual observed clearance versus patient body weight (upper panel) and LY3022855 dose (lower panel) for Study JSCA.

These updated results indicate an apparent lack of relationship between patient body weight and LY3022855 CL (**Figure 2**), consistent with previous analyses. Moreover, the PK of LY3022855 in patients receiving a non-weight-based dose of 100 mg QW (Cohort 6a) and the weight-based dose of 1.25 mg/kg QW (Cohort 5) appears comparable (**Figure 1**). The AUC_(0-τ), C_{max}, t_{max}, and t_{1/2} values are consistent between the 2 cohorts, further demonstrating a lack of a relationship between patient body weight and serum LY3022855 concentration exposure. Taken together, these analyses provide support for the exploration of LY3022855 using a non-weight-based dosing approach.

Similar findings with monoclonal antibodies have been reported by others³⁵⁻³⁸. Wang and colleagues investigated 12 monoclonal antibodies and found that fixed and body size-based

dosing perform similarly, with fixed dosing being better for 7 of 12 antibodies³⁶. In addition, they investigated 18 therapeutic proteins and peptides and showed that fixed dosing performed better for 12 of 18 in terms of reducing the between-subject variability in PK/pharmacodynamic parameters³⁷.

A fixed dosing approach is preferred by the prescribing community due to ease of use and reduced dosing errors. Given expectation of similar PK exposure and variability, we considered it feasible to switch to fixed dosing regimens.

2.5.2 LY3022855 Flat Dosing Safety

Updated safety analyses for patients treated in the flat dosing cohorts for Study JSCA (data cut off date of 06 September 2016) are available; including 3 patients treated in Cohort 6a (100 mg weekly [QW]) and 3 patients treated in Cohort 7a (150 mg QW).

LY3022855 administered at a flat dose on a weekly schedule has not resulted in any adverse events that led to permanent discontinuation of study treatment. Only one patient who received flat weekly dosing of LY3022855 experienced an AE (elevated lipase) resulting in a dose reduction. The most common treatment emergent adverse events (all grades, with a minimum incidence of 33%) for patients treated with flat weekly dosing were: anemia (4 – 67%), nausea (3 – 50%), fatigue (3 – 50%), constipation (2 – 33%), lipase elevation (2 – 33%), hypocalbuminemia (2 – 33%), hypocalcemia (2 – 33%), and back pain (2 – 33%). The majority of these TEAEs were Grade 1 or 2. The incidence of Grade 3 events were: anemia (2 – 33%), nausea (0%), fatigue (2 – 33%), constipation (0%), lipase elevation (1 – 17%), hypoalbuminemia (0%), hypocalcemia (0%), and back pain (0%). A summary of all-cause serious treatment-emergent adverse events for flat doses are presented in the table below. Two patients treated at a dose of 100mg QW experienced 4 serious treatment-emergent AEs. One patient experienced an SAE of pulmonary hemorrhage (Medical Dictionary for Regulatory Activities Preferred Term [MedDRA PT]), and the second patient, experienced SAEs of abdominal discomfort, C-reactive protein increased, and upper gastrointestinal (GI) hemorrhage (all are MedDRA PTs).

No DLT events were reported for patients treated at a dosage of 100mg QW. One out of three patients treated at a dosage of 150mg QW experienced a DLT event of Grade 3 serum creatine kinase (CK) elevation associated with elevated urine and serum myoglobin. As a result of this one DLT, 3 additional patients are planned to be enrolled to the 150mg QW dose level.

Dose levels for LY3022855 in this protocol are detailed in **5.1** and are not planned to exceed the 100 mg weekly dose that has thus far been shown to be tolerable in study JSCA. As a result 50 mg QW is an appropriate initial dose for LY3022855 for this study.

Table 9: Study JSCA: Summary of Serious Treatment-Emergent Adverse Events for Flat Doses

Summary of Serious Treatment-Emergent Adverse Events for Flat Dose. - Study I5F-IE-JSCA/CP24-1001 Safety Population

13:51 07SEP2016 TDTM

		100 mg week (N=3) n(%)	ly	150 mg weekly (N=3) n(%)			
SOC/Preferred Term	All Grades	Grade =3	Grade >=4	All Grades	Grade =3	Grade >=4	
Patients with any AE	1 (33.3)	0	0	1 (33.3)	1 (33.3)	0	
Gastrointestinal disorders	0	0	0	1 (33.3)	1 (33.3)	0	
ABDOMINAL DISCOMFORT	0	0	0	1 (33.3)	1 (33.3)	0	
UPPER GASTROINTESTINAL HAEMORRHAGE	0	0	0	1 (33.3)	1 (33.3)	0	
nvestigations	0	0	0	1 (33.3)	0	0	
C-REACTIVE PROTEIN INCREASED	0	0	0	1 (33.3)	0	0	
espiratory, thoracic and mediastinal	1 (33.3)	0	0	0	0	0	
PULMONARY HAEMORRHAGE	1 (33.3)	0	0	0	0	0	

Note 1: For each SOC and Preferred Term, each patient was counted only once according to the worst grade of the TEAE. Note 2: All Grades column includes patients with missing CTC grades as well.

Data cut-off date: September 6, 2016.

2.6 Correlative Studies Background

Use of immune and targeted therapies in patients with genomically complicated tumors presents a variety of confounding variables that could contribute to success or failure of the therapy. Correlative studies are designed to both enable better understanding of the possible reasons that LY3022855 in combination with vemurafenib and cobimetinib may prove to be effective or ineffective in individual patients, and to enable the development of more effective targeting strategies in the future.

Collection of Tumor Tissue

In order to retrospectively explore the determinants of response and resistance to LY3022855 combination therapy, archival tumor tissue will be collected at baseline from all patients enrolling to the trial. In addition, optional fresh tumor biopsies will be obtained from patients enrolled to either the phase I or phase II portion of the trial. These biopsies will be obtained ontreatment and again at the time of disease progression. The genetic and immune characteristics identified in the tumor tissue will be correlated to clinical outcome.

Analysis of tumor tissue samples taken at distinct points enables addressing of key questions including: (1) the genomic lesions and immune cell presence at baseline in samples studied and their potential impact upon response, (2) the identification of immediate pathways/gene expression programs activated by tumors following LY3022855 combination therapy, and (3) mechanisms of acquired resistance to therapy.

The first correlative question relates to the genetic and immune diversity of the patients enrolled in this study. It is the anticipation that most patients on this study will have had their tumor genomically characterized by either the OncoPanel test at DFCI/BWH (a custom hybrid capture panel which via next-generation sequencing will identify mutations and copy-number alterations in cancer associated genes) or via another CLIA-certified method at the time of enrollment. The archival tissue collected will be analyzed to look at the TAMs present at baseline. Macrophages are among the most abundant normal cells in the tumor microenvironment. Substantial evidence has indicated that macrophages adopt a pro-tumoral phenotype, suppressing T cell response and promoting tumor progression via angiogenesis, tumor cell invasion, motility, intravasation, and promotion of persistent growth³². The levels of certain TAMs present at baseline can be correlated to the clinical response observed with the combination therapy, and this data may enable us to identify immune characteristics that may also impact clinical response.

Another key rationale for performance of biopsies in patients after initiating drug therapy is to address mechanisms of resistance to LY3022855 combination therapy. The emergence of resistance to therapy is a profound problem in oncology. Such resistance can follow not only acquisition of secondary mutations but also from the ability of cancer cells to activate immediate compensatory signaling tracts following targeted inhibition of a key pathway³⁹. Identification of these compensatory reactions is a necessary step in order to design subsequent rational therapies that may lead to even more durable and long-lasting clinical benefit. The optional on-treatment tissue samples will be examined for changes in MAPK activation as well as levels of TAMs and tumor immune infiltrates.

Optional biopsies obtained at the time of disease progression will be used to characterize the change in the tumor at the time of resistance. Such changes could stem from the acquisition of novel genomic alterations, from activation of other signaling pathways, or the production of anti-inflammatory and immunosuppressive mediators. Biopsies obtained at progression will be analyzed for MAPK reactivation, other mechanisms of resistance (e.g., alternate kinase domain mutations), and tumor immune infiltrates. The information collected from these biopsies will be vital to understanding the methods of resistance to the combination therapy and planning subsequent treatment strategies in this population.

Collection of Blood

Cell-free DNA (cfDNA) will be collected and analyzed for *BRAF* V600E or V600K mutations. Levels of tumor DNA will decline longitudinally over time if there is a response to the treatment administered. To further assess this concept, plasma will be collected from participants to evaluate whether circulating free plasma DNA declines with the administration of LY3022855, vemurafenib, and cobimetinib and this information will be compared to clinical outcome.

Blood samples will also be collected to look at circulating immune cells including MDSCs. MDSCs are a heterogeneous group of myeloid-derived cells which are greatly expanded in experimental models of cancer. Studies in humans carried out thus far have reported an increased frequency as well as immune-suppressive activity in some of the myeloid-derived subsets of MDSCs present in the peripheral blood of patients with cancer. In the case of metastatic melanoma, both monocytic as well as granulocytic blood MDSCs with immune-suppressive function have been studied independently and proposed to exert an immune-regulatory role⁴⁰. To further explore the relationship of circulating immune cells including MDSCs and their potential correlation to clinical outcomes, peripheral blood levels will be serially collected from patients enrolled to the trial.

3. PARTICIPANT SELECTION

3.1 Eligibility Criteria

Baseline evaluations are to be conducted within 14 days prior to start of protocol therapy, with the exception of the informed consent, echocardiogram, ophthalmologic exam, and baseline tumor imaging which may be obtained up to 28 days prior to the start of protocol therapy.

3.1.1 For enrollment to the phase I portion: participants must have a histologically confirmed melanoma with a *BRAF* V600E or *BRAF* V600K mutation (identified via NextGen sequencing using the DFCI/BWH OncoPanel or any CLIA-certified method) that is metastatic or unresectable and for which standard curative measures do not exist or are no longer effective.

- 3.1.2 For enrollment to the phase II portion: participants must have a histologically confirmed melanoma with a *BRAF* V600E or *BRAF* V600K mutation (identified via NextGen sequencing using the DFCI/BWH OncoPanel or any CLIA-certified method) and cannot have received prior BRAF or MEK inhibitor therapy.
- 3.1.3 Participants enrolling to the phase I portion of the trial must have evaluable or measurable disease (see 11 for definitions).
- 3.1.4 Participants enrolling to the phase II portion of the trial must have measurable disease, defined as at least one lesion that can be accurately measured in at least one dimension (longest diameter to be recorded for non-nodal lesions and short axis for nodal lesions) as ≥ 10 mm with spiral CT scan, MRI, or calipers by clinical exam. See 11 for the evaluation of measurable disease.
- 3.1.5 Age ≥ 18 years. As no dosing or adverse event data are currently available in participants < 18 years of age, children are excluded from this study but will be eligible for future pediatric trials.
- 3.1.6 ECOG performance status 0 1 (see **APPENDIX A** PERFORMANCE STATUS CRITERIA).
- 3.1.7 Participants must have normal organ and marrow function as defined below:

Absolute neutrophil count
 Platelets
 Hemoglobin
 ≥ 1.5 K/uL
 ≥ 100 K/uL
 ≥ 9 g/dL

- Total bilirubin $\leq 1.5 \times \text{institutional upper limit of normal (ULN)}$

AST(SGOT)/ALT(SGPT) ≤ 2.5 × institutional ULN
 Serum creatinine ≤ 1.5 × institutional ULN

- PT-INR $\leq 1.5 \times \text{institutional ULN (for participants on }$

anticoagulation therapy, $\leq 1.5 \times$ their baseline value)

- aPTT $\leq 1.5 \times \text{institutional ULN (for participants on }$

anticoagulation therapy, $\leq 1.5 \times$ their baseline value)

- 3.1.8 Participants must have a left ventricular ejection fraction (LVEF) $\geq 50\%$.
- 3.1.9 Participants must have a QTc of \leq 470 msec on the screening EKG.

3.1.10 The effects of LY3022855 on the developing human fetus are unknown. For this reason and because anti-cancer agents are known to be teratogenic, women of child-bearing potential and men must agree to use adequate contraception (hormonal or barrier method of birth control; abstinence) prior to study entry and for the duration of study participation. Should a woman become pregnant or suspect she is pregnant while she or her partner is participating in this study, she should inform her treating physician immediately. Men treated or enrolled on this protocol must also agree to use adequate contraception prior to the study, for the duration of study participation, and 4 months after completion of LY3022855 administration.

- 3.1.11 Ability to understand and the willingness to sign a written informed consent document.
- 3.1.12 Participants must have archival tumor tissue available. Participants without archival tissue may be enrolled at the discretion of the principal investigator.

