11.1 Antitumor Effect – Solid Tumors

For the purposes of this study, participants should be re-evaluated for response every eight weeks. In addition to a baseline scan, confirmatory scans should also be obtained not less than four weeks following initial documentation of objective response.

Response and progression will be evaluated in this study using the new international criteria proposed by the Response Evaluation Criteria in Solid Tumors (RECIST) guideline (version 1.1) [Eur J Ca 45:228-247, 2009]. Changes in the largest diameter (unidimensional measurement) of the tumor lesions and the shortest diameter in the case of malignant lymph nodes are used in the RECIST criteria.

Participants enrolling to the phase I portion of the trial who do not have measurable disease at baseline per RECIST 1.1 guidelines may be enrolled if they have evaluable disease. Evaluable disease includes non-measurable disease: small lesions (longest diameter <10 mm or pathological lymph nodes with ≥10 to <15 mm short axis), bone lesions, leptomeningeal disease, ascites, pleural/pericardial effusions, lymphangitis cutis/pulmonitis, inflammatory breast disease, and abdominal masses that cannot be accurately measured by CT or MRI are all considered non-measurable. For the purposes of the phase I portion of the trial a participant who exhibits one or more non-measurable disease parameters but does not meet the definition for measurable disease may be enrolled assuming that they meet the other eligibility requirements of the protocol.

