11.1.1 Definitions

Evaluable for Target Disease response. Only those participants who have measurable disease present at baseline, have received at least one cycle of therapy, and have had their disease re-evaluated will be considered evaluable for target disease response. These participants will have their response classified according to the definitions stated below. (Note: Participants who exhibit objective disease progression prior to the end of cycle 1 will also be considered evaluable.)

Evaluable Non-Target Disease Response. Participants who have lesions present at baseline that are evaluable but do not meet the definitions of measurable disease, have received at least one cycle of therapy, and have had their disease re-evaluated will be considered evaluable for non-target disease. The response assessment is based on the presence, absence, or unequivocal progression of the lesions.

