11.1.2 Disease Parameters

Measurable disease. Measurable lesions are defined as those that can be accurately measured in at least one dimension (longest diameter to be recorded) as ≥ 20 mm by chest x-ray or ≥ 10 mm with CT scan, MRI, or calipers by clinical exam. All tumor measurements must be recorded in millimeters (or decimal fractions of centimeters).

Note: Tumor lesions that are situated in a previously irradiated area will not be considered measurable.

Malignant lymph nodes. To be considered pathologically enlarged and measurable, a lymph node must be ≥ 15 mm in short axis when assessed by CT scan (CT scan slice thickness recommended to be no greater than 5 mm). At baseline and in follow-up, only the short axis will be measured and followed.

Non-measurable disease. All other lesions (or sites of disease), including small lesions (longest diameter <10 mm or pathological lymph nodes with ≥10 to <15 mm short axis), are considered non-measurable disease. Bone lesions, leptomeningeal disease, ascites, pleural/pericardial effusions, lymphangitis cutis/pulmonitis, inflammatory breast disease, abdominal masses (not followed by CT or MRI), and cystic lesions are all considered non-measurable

Note: Cystic lesions that meet the criteria for radiographically defined simple cysts should not be considered as malignant lesions (neither measurable nor non-measurable) since they are, by definition, simple cysts.

'Cystic lesions' thought to represent cystic metastases can be considered as measurable lesions, if they meet the definition of measurability described above. However, if non-cystic lesions are present in the same participant, these are preferred for selection as target lesions.

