Target lesions. All measurable lesions up to a maximum of 2 lesions per organ and 5 lesions in total, representative of all involved organs, should be identified as **target lesions** and recorded and measured at baseline. Target lesions should be selected on the basis of their size (lesions with the longest diameter), be representative of all involved organs, but in addition should be those that lend themselves to reproducible repeated measurements. It may be the case that, on occasion, the largest lesion does not lend itself to reproducible measurement in which circumstance the next largest lesion which can be measured reproducibly should be selected. A sum of the diameters (longest for non-nodal lesions, short axis for nodal lesions) for all target lesions will be calculated and reported as the baseline sum diameters. If lymph nodes are to be included in the sum, then only the short axis is added into the sum. The baseline sum diameters will be used as reference to further characterize any objective tumor regression in the measurable dimension of the disease.

Non-target lesions. All other lesions (or sites of disease) including any measurable

lesions over and above the 5 target lesions should be identified as **non-target lesions** and should also be recorded at baseline. Measurements of these lesions are not required, but the presence, absence, or in rare cases unequivocal progression of each should be noted throughout follow up.

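### Phase II criterion 3.1.4 counts a lymph node of 10 mm short axis as measurable, while section 11 classes nodes of 10 to under 15 mm as non-measurable, so a patient with no target lesion can be enrolled and counted in ORR

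*Combined protocol and SAP*

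**What the plan says.** - **Entry, phase II (3.1.4).** At least one measurable lesion is required. The criterion uses longest diameter for non-nodal lesions and, for nodes, "short axis for nodal lesions) as ≥ 10 mm with spiral CT scan, MRI, or calipers by clinical exam". It closes with "See 11 for the evaluation of measurable disease".
- **Nodes (11.1.2).** To be measurable, "a lymph node must be ≥ 15 mm in short axis when assessed by CT scan". The non-measurable class includes "pathological lymph nodes with ≥10 to <15 mm short axis), are considered non-measurable disease". This second statement names no imaging modality.
- **Entry without measurable disease (11.1).** "Participants enrolling to the phase I portion of the trial who do not have measurable disease at baseline" may enter if they have evaluable disease. Nothing equivalent is given for phase II.
- **Target lesions (11.1.2).** These are drawn from measurable lesions only: "All measurable lesions up to a maximum of 2 lesions per organ and 5 lesions in total".
- **Evaluability (11.1.1).** One class is tied to target lesions: "Only those participants who have measurable disease present at baseline, have received at least one cycle of therapy, and have had their disease re-evaluated". A separate non-target class covers this group: "Participants who have lesions present at baseline that are evaluable but do not meet the definitions of measurable disease".
- **Scoring without target lesions (11.1.3.4, Table 25).** The outcomes are CR, non-CR/non-PD, not evaluated and PD. There is no PR.
- **Analysis set (13.3, 13.4.2).** Primary and secondary analyses use eligible patients who started therapy, and all eligible participants are assessed for response. ORR is reported with a 90% exact interval, said to be at most 0.35 wide with 25 patients.
- **Calipers (11.1.3).** Palpable nodes of at least 10 mm by calipers are accepted as measurable.

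**The concern.** Two current sections give different cutoffs for the same measurement. A patient whose only disease lies in nodes of 10 to under 15 mm on CT meets the phase II entry criterion but, by section 11, has none of the measurable disease that the criterion is meant to secure.

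If enrolled, that patient counts in the ORR denominator but can be scored a responder only through a complete response. If someone later applies section 11 to decide who was eligible, the same patient could be removed from the ORR set after outcomes are known. In a single-arm phase II of 25 patients, the denominator should not rest on a choice the plan leaves open.

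**Working it through.** **1. The cutoffs side by side**

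| Node measured by | 3.1.4 (phase II entry) | Section 11 |
|---|---|---|
| CT | ≥ 10 mm short axis | ≥ 15 mm short axis (11.1.2); 10 to < 15 mm non-measurable |
| MRI | ≥ 10 mm short axis | 15 mm not stated for MRI; 10 to < 15 mm non-measurable, no modality named |
| Calipers | ≥ 10 mm | ≥ 10 mm for palpable nodes (11.1.3), against the same modality-free non-measurable class in 11.1.2 |

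The conflict is explicit for CT. For MRI it rests on the modality-free sentence. For calipers, section 11 is not uniform within itself.

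**2. One patient followed through the plan: a single 12 mm node on CT, no other disease**

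- 3.1.4: eligible, since 12 ≥ 10.
- 11.1.2: not measurable, since 12 < 15, so there is no target lesion.
- 11.1.1: not evaluable for target disease response; falls in the non-target class.
- Table 25: can be scored CR but not PR.
- 13.3 and 13.4.2: counted in ORR as an eligible patient.

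The missing PR category matters when shrinkage is substantial but incomplete. Take two nodes of 14 mm each that shrink to 9 mm and 10.5 mm. The sum falls from 28 to 19.5 mm, and (28 − 19.5)/28 = 30.4%. On target lesions that would meet the 30% PR rule in 11.1.3.1. As non-target disease it is non-CR/non-PD, because one node is still at or above 10 mm (11.1.3.2).

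**3. When the denominator changes**

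- Section 11 used at screening: the patient is not enrolled, another fills the place, and n stays 25.
- 3.1.4 used at both registration and analysis: the patient is kept and n is 25.
- 3.1.4 used at registration and section 11 at analysis: the patient may be treated as ineligible and dropped, so n falls below 25.

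**4. Size**

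The plan's own figure first. The maximum width of the 90% Clopper-Pearson interval over all possible response counts at n = 25 is 0.3535 (at 12 responders), which agrees with the stated 0.35 to two decimals. At n = 24 it is 0.361 and at n = 23 it is 0.369.

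The documents do not give the number of affected patients, k. Assume k = 1 or 2, that these patients do not respond, and that about two thirds of the others do. The last assumption is close to the 64–68% that section 2.1 gives for BRAF/MEK combinations in general; it is not a figure for small-node disease. With r responders among the other 25 − k:

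- ORR if dropped = r/(25 − k); ORR if kept = r/25.
- k = 1: 16/24 = 66.7% against 16/25 = 64.0%, a difference of 2.7 points.
- k = 2: 15/23 = 65.2% against 15/25 = 60.0%, a difference of 5.2 points.

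**The case against.** The strongest reply is that the text already ranks the two sections. Phase I criterion 3.1.3 sends the reader to section 11 for definitions. Phase II criterion 3.1.4 supplies its own definition and cites section 11 only for evaluation. On that reading 3.1.4 governs entry, section 11 governs response assessment, the patient is eligible, and the ORR denominator is settled. This is plausible, but no section states the precedence. Even if it is accepted, the plan enrols as having measurable disease a patient whom section 11 treats as having none.

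The practical safeguards are also real. Registration is within DF/HCC institutions, an investigator confirms eligibility and a checklist is completed (4.1), and scans are read centrally (11.1.6). However, the checklist is not in the documents, so its cutoff is unknown, and central reading is described for response review, not for screening.

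Some stronger readings are tempting but not supported:

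- **That each such patient moves ORR by 4 points (1/25) because of the conflict.** That is the gap between scoring a retained patient as a responder or as a non-responder. It reflects the patient's outcome under one eligibility rule. The effect of the conflict is the dropped-versus-kept difference.
- **That the ORR set necessarily shrinks.** It does so only if different sections are applied at registration and at analysis.
- **That ORR is biased in a known direction.** The documents do not give the number of these patients or their response rate.
- **That the primary endpoint is compromised.** The eligible set in 13.3 also serves PFS, but the PFS power calculation has no measurability input, and Table 25 provides for progression without target lesions.
- **That 11.1.2 states 15 mm for MRI.** It names CT only.

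**Conclusion.** The inconsistency is real and in current text, and it is minor. As written, 3.1.4 can admit a phase II patient with no target lesion who counts in ORR but cannot be scored PR. If the two sections are applied at different stages, that patient could be dropped instead.

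The illustrated size, 2.7 points for one patient and 5.2 for two, rests on assumed numbers and on those patients not responding. The true number may be zero. Either shift is small beside a 90% interval that can be about 35 points wide, and ORR is a secondary endpoint reported descriptively without a test.

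**What to change.** Before phase II enrolment:

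1. Amend 3.1.4 to match the nodal definition in section 11: at least one non-nodal lesion of at least 10 mm longest diameter, or a lymph node of at least 15 mm short axis on CT.
2. State in both 3.1.4 and 11.1.2 that the same nodal cutoff applies to MRI.
3. Reconcile both with the caliper line in 11.1.3, so that one rule covers nodes measured only by calipers.
4. Check that the eligibility checklist in 4.1 uses the amended text.

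The cost is a short wording amendment and a checklist check. The planned 25 patients and the PFS power calculation do not change. The downside is that patients whose only disease is nodes of 10 to under 15 mm become ineligible for phase II; the documents do not say how many that would be. Whether some patients with caliper-only nodes are also affected depends on how item 3 is settled.
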